9.7.3 Safety Analysis

All adverse events and adverse drug reactions collected per study protocol will be included and summarised in the interim safety analysis and in the final study report.

9.8 QUALITY CONTROL

This NIS will be conducted according to Guidelines for Good Pharmacoepidemiology SPractice (GPP) and Good Pharmacovigilance Practice (GVP), and also will be conducted following the standards of International Council for Harmonisation/Good Clinical Practice (ICH/GCP) (7) in accordance with local regulations, particularly regarding ethics, protection of patient's privacy, and processing of data. All necessary related data and documents will be made available for inspection.

All entries in the eCRFs will be stored in a database. The structure of the database is based on the division into sections and entry fields defined in the eCRFs. To improve and ensure data quality, data checks will be performed automatically in the eCRFs directly on electronic entry at the study site.

Plausible value ranges for numerical data entries, and logical data and list entries will be filed in the eCRFs. The tests for consistency and completeness based on this will be performed during entry in the eCRFs. The validity of the recorded data will, therefore, be ensured by the validations incorporated in the documentation system, which highlight incorrect or implausible entries to the data entry clerk/doctor.

If corrections are necessary after the data are saved, these will be documented in an audit trail.

For further quality assurance of the documented patient observations, a sample-size based source data verification will be performed on about 30% of patients included (not including the additional data collected for follow-up analyses). In addition, a risk-based monitoring will be taken for critical data and documents of all patients, and 100% of these critical data and documents will be verified.

A quality assurance audit/inspection of this study may be conducted by the sponsor or sponsor's designees or by independent ethics committees (IECs) or by regulatory authorities. The quality assurance auditor will have access to all medical records, the investigator's study-related files and correspondence, and the informed consent documentation of this study.

9.9 LIMITATIONS OF THE RESEARCH METHODS

Prospective data collection brings its own challenges. Even with a careful controlled design, there may be various sources of bias that can completely distort the results. In this study, potential limitations of the study design can be listed as:

9.9.1 Lost to follow-up

All patients will be followed up until the event of OS. If a patient misses more than 1 clinic care visit, the site will attempt to communicate with the patient and document the patient's reason for not returning. Sites will be requested to contact patients at various times of the day and evening and on different days of the week. If the patient cannot be contacted after the due diligence process, the treating physician will attempt to contact the patient's designated secondary contacts, including the patient's general practitioner and next-of-kin or out-of-household contacts to obtain information on the patient's whereabouts and vital status. If the patient's care has been transferred to another healthcare professional, the treating physician at the enrolling site will be responsible for obtaining the required follow-up information from the new treating physician. Patients who do not return for at least 2 scheduled visits, and for whom no information is available will be considered lost to follow-up and will be censored at time of last visit or last known contact with the healthcare provider.. Follow-up information collecting could be accepted by phone call if the information is available and complete.

9.9.2 Channelling bias

Channelling bias can occur due to preferential prescribing in relation to different risks for the events of interest. For example, if afatinib therapy would be prescribed more often compared with other treatments to high risky Chinese patients with EGFR mutation positive NSCLC (e.g., patients in this study are more severe than other Chinese EGFR mutation positive NSCLC patients or with more comorbidities at baseline). Thus, more incidences of outcome events were expected in the group with afatinib therapy (e.g., the incidence rates of AEs/ADRs will be affected). Furthermore , all patients who fulfil eligibility criteria and provide written informed consent will be enrolled. as patients with severe disease or other disabilities (eg those who are likely to have poorer outcomes) may be excluded from the study. This study is descriptive only and there are no comparisons between groups. To assess the presence of the bias, we plan to use the data from study 1200-0066 to put the results into perspective to compare baseline demographic and clinical characteristics of the NSCLC patients. Through this, we can verify that safety or efficacy difference is due to patient baseline characteristics or the sequential therapy.

9.9.3 Study Sample Size

76 patients were enrolled in this study, this is a small sample size which may impact the assessment of study outcomes. A sample size of 76 patients is expected to ensure an 80% chance to observe the width of the 90% CI of median TOT of afatinib smaller than or equal to 11 months.

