Name of finished medicinal product: Giotrif®				
Name of active ingredient: Afatinib				

withdraw before the end of study will be censored at the time of last known contact.
 
Secondary outcomes
 
Overall survival (OS) from the start of afatinib until the date of death, loss to follow up (including patient withdrawal) or end of study period
 
Objective response rate (ORR), [objective response is defined as best overall response of complete response (CR), partial response (PR)] according to RECIST 1.1 with afatinib first-line therapy
 
Adverse events (AEs), serious adverse events (SAEs), afatinib-related AEs (ADRs) as indicated by incidence, seriousness and intensity graded according to United States (US) national cancer institute's (NCI) common terminology criteria for AEs version 5.0 (CTCAE Version 5.0)
 
Further outcome
 
Resistance mechanisms (Type and proportion:T790M,etc) after afatinib first-line treatment.
				
Data sources:	
Data for this study will be obtained via the following sources:
 
- Patient medical information: The investigator or authorized medical staff will record clinical and treatment data from patients' medical records into an electronic case report form (eCRF) at baseline and at every visit up to end of the follow up period (refer to Section 9.4)			
Study size:	76 patients			
Study duration:	The duration of data collection for an individual patient will be a maximum of approximately 33 months, It is anticipated that all data collection for this study started from May 2020(first patient enrolled) and will continue until December 2023 (two years after the last patient was enrolled)			
Data analysis:	
Time on treatment (TOT) will be analysed using Kaplan-Meier method, and the median Time on Treatment (TOT) along with two-sided 90% confidence interval (CI) will be calculated. Overall survival (OS) will be analysed similarly.
 
Objective response rate (ORR) and acquired resistance mutation type, and AEs will be summarised descriptively by frequency and proportions.
			
Milestones:				
IRB/IEC Approval: May 2020				
First Patient In: May 2020				

Name of company: Boehringer Ingelheim		
Name of finished medicinal product: Giotrif®		
Name of active ingredient: Afatinib Last Patient In: Dec 2021 Interim Analysis: Dec 2022 Last Patient Out: Dec 2023 Database Locked: Mar 2024 Final NIS Report: Jun 2024		

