9.5 STUDY SIZE

Seventy-six patients will be included in this study.

Based on LUX-Lung trials, we assume the median time on treatment (TOT) on afatinib to be 12 months in this study. Assuming that the time on treatment (TOT) follows an exponential distribution, it is expected to have 35 events till 2 years after last patient in, given total sample size equal to 76, considering a 30% drop out rate.

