7.6 PRIMARY ANALYSES

All patients treated with afatinib will be included in the analysis of the primary outcome, Time on Treatment (TOT) on afatinib.

The TOT with afatinib is defined as time from the start of afatinib to last dose date of afatinib or death date by any cause, which comes first.

Refer to Table 7.6: 1 for the rules for determining TOT with afatinib event or censoring date. The analysis of TOT with afatinib will be performed on Treated Set (TS). Those analyses will be conducted as one of the interim analyses mentioned in [section 7.11](#).

Table 7.6: 1 Rules for determining TOT event or censoring date

Rule #	Situation	Outcome	Date of event or censoring
1	Patients lost to follow up without providing end date of treatment during afatinib treatment period	censor	Date of last known date of contact during afatinib treatment period
2	Patients still receive ongoing first-line afatinib treatment at end of study period	censor	Date of last known date of contact during first line afatinib treatment period

Proprietary confidential information © 2024 Boehringer Ingelheim International GmbH or one or more of its affiliated companies

Rule #	Situation	Outcome	Date of event of censoring
3	Other situations	event	Date of last treatment during first line afatinib treatment period

The last known date of contact will derive as follows:

For subjects who withdrew from study or became lost to follow-up, the date last known of contact will be based on the last assessment date/visit date or the date of the last dose of study drug or end of study date, whichever occurs later.

If last known of contact date is later than cut-off date, use cut-off date as last known of contact date.

Kaplan-Meier estimates and two-sided 90% confidence intervals for the 25th, median, and 75th percentiles of the survival distribution will be calculated, the Brookmeyer-Crowley method^[4] based on log-log transformation will be used to construct the 90% CI, the standard error of the Kaplan-Meier quartile estimates will be estimated using Greenwood's formula. Kaplan-Meier curves will also be produced.

For the purpose of calculating TOT, incomplete first line afatinib treatment end dates will be imputed as below:

If month and year are present and day is missing:

- If year=year of first dosing and
 - If month = month of first dose then set day to day of first dose
 - If month > month of first dose then set day to first day of month

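### The 80% chance of an 11-month-wide 90% CI (Protocol 9.9.3) does not follow from the inputs in 9.5 under independent 30% drop-out, and does not fit with the 35 expected events

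*Protocol*

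**What the plan says.** Protocol 9.5 fixes the size ("Seventy-six patients will be included in this study") and gives the planning inputs. For the median it says "we assume the median time on treatment (TOT) on afatinib to be 12 months in this study". The distribution is taken to be exponential. For the event count it says "it is expected to have 35 events till 2 years after last patient in", and this count is reached "considering a 30% drop out rate". It gives neither a time unit nor a mechanism for the 30%.

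Protocol 9.9.3, under limitations, gives the precision claim: an "80% chance to observe the width of the 90% CI of median TOT of afatinib smaller than or equal to 11 months". It describes no calculation method.

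The milestones run from "First Patient In: May 2020" to last patient in December 2021 and last patient out in December 2023. Protocol 9.7.1 and SAP 7.6 both use a two-sided 90% interval. SAP 7.6 names Brookmeyer-Crowley limits and says of them: "based on log-log transformation will be used to construct the 90% CI".

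**The concern.** The width of a Kaplan-Meier interval for a median depends on the number of patients, the event hazard and how much follow-up is lost to censoring. Section 9.5 gives all of these except the form of the drop-out, so 9.9.3 can be checked for each ordinary reading of the 30%. On those readings the 90% interval comes out clearly narrower than 9.9.3 says, and more events are expected than 9.5 says.

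At stake is how the primary result is read. A reader who takes 11 months as the planned precision would see a realised 90% interval of 10 to 11 months as ordinary. With independent 30% drop-out, a width above 11 months would occur in only about 4 to 11% of studies, so a width near 11 would point to heavier censoring or more heterogeneity than planned.

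**Working it through.** **Inputs.** N = 76, exponential with median 12 months, 30% drop-out, and cut-off 24 months after last entry (Protocol 9.5). Accrual from May 2020 to December 2021 is 19 months, and cut-off is at month 43 (Protocol 6). Uniform entry is my assumption.

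**Step 1: hazards.**
- Event hazard: λ = ln 2 / 12 = 0.0578 per month.
- Drop-out hazard at 30% per year: γ = −ln(0.7)/12 = 0.0297 per month.
- Drop-out hazard at 30% by 24 months: γ = −ln(0.7)/24 = 0.0149 per month.

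**Step 2: the plan's 35 events.** With s = λ + γ,

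P(event) = (λ/s) × [1 − (e^(−24s) − e^(−43s)) / (19s)].

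- 30% per year: s = 0.0875; 0.660 × (1 − 0.0597) = 0.621; × 76 = 47.2 events.
- 30% by 24 months: s = 0.0726; 0.795 × (1 − 0.0949) = 0.720; × 76 = 54.7 events.
- 30% give no data: γ = 0; P = 0.848; × 53 = 45.0 events.
- Solving 76 × P = 35 gives γ = 0.0651 per month. That is 1 − e^(−12 × 0.0651) = 54% drop-out per year, with 52% of patients observed to drop out.

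The 35 events are therefore not reproduced on any of these three readings of 30%.

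**Step 3: the plan's 80% and 11 months.** There is no simple closed form, so I used Monte Carlo simulation with several thousand runs per row. Limits are Brookmeyer-Crowley log-log with Greenwood variance, and an upper limit that cannot be estimated counts as wider than 11 months. Simulation error is about half a point per run (√(0.8 × 0.2/6000) = 0.5%), and repeat runs differ by about one point.

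| Drop-out model | Expected events | P(90% CI ≤ 11 m) | 90% CI width met with 80% probability | P(95% CI ≤ 11 m) |
|---|---|---|---|---|
| 30% by 24 months | 55 | 96% | 8.6 m | 87% |
| 30% per year | 47 | 91% | 9.4 m | 79–80% |
| 30% give no data (n = 53) | 45 | 89% | 9.9 m | 69% |
| Exponential, tuned to mean 35 events (54% per year) | 35 | 74% | 12.0 m | 56% |
| Same, given exactly 35 events | 35 | 78% | 11.3 m | 58% |
| 30% of patients censored uniformly within their own time on study (not independent) | 45 | 80% | 10.9 m | 59% |

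The first three rows are the ordinary independent readings of the stated 30%, and none gives 80% at 11 months. A linear instead of a log-log interval moves the 30%-per-year figure only to about 92%. Capping each patient at the 33 months in Protocol 9.2.2 leaves it at about 92% and 9.3 months.

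**The case against.** The strongest reply is that 9.5 states 35 events, and that a fair test of 9.9.3 must honour it. At 35 events the 90% interval meets 11 months in 74 to 78% of runs, close to the stated 80%. This is true, but 9.5 presents the 35 as a result of 30% drop-out, and it takes about 54% per year to get there. Honouring the 35 means giving up the 30% as ordinarily read.

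The second reply is that the 30% has no stated unit or mechanism, so other models are open. Three come near:
- Censoring 30% of patients within their own time on study gives 80% and 10.9 months. This is not independent censoring: it biases the Kaplan-Meier median upward (about 14.9 months in a large sample, not 12), and it yields 45 events.
- 30% per six months gives about 77 to 78% and 36.6 events. That is 1 − 0.7² = 51% per year, and no passage suggests a six-month unit.
- Counting drop-out twice (53 patients and 30% by 24 months) gives 83% and 38 events.

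It stands, therefore, that the stated precision can be reached. It is not reached by an ordinary independent 30% with the stated follow-up.

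A third reply also stands. If drop-out is 30%, the true chance exceeds 80%, so the claim errs on the safe side. The study is descriptive, and no document uses 11 months as an acceptance limit.

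A reader might go further and infer that 80% and 11 months is a 95% figure left under a 90% label, since the SAP history records a change from 95% to 90% in section 7.6. The documents do not support this. That entry mentions neither the width nor the sample size. The 95% match appears at about 30% per year (or 30% observed drop-out), while the other rows of the table give 56 to 87%. At 35 events a 95% label would be plainly wrong.

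**Conclusion.** The concern holds as an inconsistency between Protocol 9.5 and 9.9.3. Under independent drop-out of 30% per year, 30% over 24 months or 30% without data, the chance that the 90% interval is at most 11 months wide is about 89 to 96%, not 80%. The width met with 80% probability is 8.6 to 9.9 months, not 11, and the expected events are about 45 to 55, not 35. On those readings, 30% drop-out, 35 events and 80% at 11 months cannot all be right.

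This rests on uniform accrual over 19 months and on independent censoring. The documents do not say which figure is the wrong one. A carry-over from a 95% interval is a possible explanation only. The consequence is moderate: the sample size is not shown to be inadequate, but the only precision benchmark for the primary outcome cannot be relied on as written.

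**What to change.** State in 9.5 the drop-out model, its time unit and the accrual assumption, and in 9.9.3 the interval method and how the probability was obtained. Then recompute the two sections together:
- If 30% is per year: about 47 expected events and an 80% chance that the 90% interval is at most 9.4 months wide.
- If 30% is over 24 months: about 55 events and 8.6 months.
- If 30% of patients give no data: about 45 events and 9.9 months.
- If 35 events and 80% at 11 months are kept: state the drop-out rate or rule that they require, about 54% per year for 35 events under exponential drop-out (which gives 74 to 78%), and justify it.

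Do not relabel the figure as a 95% interval unless the original calculation shows that it was one. The cost is one or two sentences in the protocol, the SAP or the study report, and a short simulation. No patients, data or changes to the analysis are needed.

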9.10 OTHER ASPECTS

9.10.1 Data quality assurance

A quality assurance audit/inspection of this study may be conducted by the sponsor or sponsor's designees or by IECs or by regulatory authorities. The quality assurance auditor will have access to all medical records, the investigator's study-related files and correspondence, and the informed consent documentation of this study.

9.10.2 Patient completion

The collection of the data of patients will continue until the end of data collection or withdrawal of consent (if applicable) which occurs first.

9.10.3 Completion of study

The end of the study will occur when the data is collected from the last patient's data. No further data will be collected afterwards.

9.10.4 Study records

eCRFs for individual patients will be provided by the sponsor via remote data capture.

9.10.4.1 Source documents

Source documents provide evidence for the existence of the patient and substantiate the integrity of the data collected. Source documents are filed at the investigator's site.

Data reported on the eCRFs that are transcribed from source documents must be consistent with the source documents, or the discrepancies must be explained. The investigator may need to request previous medical records or transfer records, depending on the study; also current medical records must be available.

9.10.4.2 Direct access to source data and documents

The investigator/institution will permit study-related monitoring, audits, IEC review, and regulatory inspection, providing direct access to all related source data/documents. eCRFs and all source documents, including progress notes and copies of laboratory and medical test results, must be available at all times for review by the sponsor's clinical study monitor, auditor and inspection by health authorities (e.g.,NMPA). The CRA/CTM and auditor may review all eCRFs, and written informed consents. The accuracy of the data will be verified by reviewing the documents described in [Section 9.10.4.1](#).

9.10.5 Protocol deviations

NA

9.10.6 Compensation available to the patient in the event of study related injury

NA

9.11 BIAS

Methodological efforts have been taken to minimise channelling bias and attrition bias: these efforts including using the data from study 1200-0066 to assess potential channelling and to put the results into perspective, which will help address this issue. Details of bias can be referred to [Section 9.9](#).

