5. OUTCOMES

5.1 PRIMARY OUTCOMES

- Time on treatment of afatinib (ToT) as first-line therapy in advanced non-small cell lung cancer patients with EGFR mutation. Time on treatment is defined from the start of afatinib treatment until the end of the afatinib treatment or death date by any cause. Patients that are lost to follow up or withdraw before the end of study will be censored at the time of last known contact.

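### Loss to follow-up on afatinib is censored at last known contact with no visible analysis of how far the primary median TOT depends on it; SAP 5.1 and Table 7.6:1 also disagree on withdrawn patients

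*Protocol*

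**What the plan says.** **Censoring rule.** SAP 5.1 states: "Patients that are lost to follow up or withdraw before the end of study will be censored at the time of last known contact". In Table 7.6:1 of SAP 7.6, Rule 1 censors this group: "Patients lost to follow up without providing end date of treatment during afatinib treatment period". Rule 2 censors patients still on afatinib at the end of the study. Rule 3 makes every other situation an event at the last treatment date. The text under the table defines last known contact, for withdrawn and lost patients, as the latest of the last assessment or visit, the last dose and the end-of-study date. An end date that cannot be imputed also leads to censoring at last known contact. Protocol 9.7.1 limits TOT censoring for loss to patients with no afatinib end date.

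**Expected loss.** Protocol 9.5 plans its event count "given total sample size equal to 76, considering a 30% drop out rate". It gives no time base and does not say whether the drop-out is from afatinib or from the study.

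**Attrition.** Protocol 9.11 says: "Methodological efforts have been taken to minimise channelling bias and attrition bias: these efforts including using the data from study 1200-0066". It then refers to Section 9.9. There, 9.9.1 describes tracing: contact attempts by the site, secondary contacts, follow-up through a new physician, and telephone. A patient counts as lost after failing to return for at least two scheduled visits with no information available. SAP 7.4, on bias, covers channelling only.

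**The concern.** Kaplan-Meier treats a patient censored on afatinib as having the same future risk of stopping as patients still under observation. TOT measures whether the patient is still taking the drug, so someone who disappears from care may also have stopped. If so, the censoring is informative and the median is too long. The rule can add to this, because it takes the latest available contact date rather than the last documented dose. The 90% CI reflects sampling error only and would not reveal the problem.

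The protection named in 9.11 does not help. A comparison of baseline characteristics with study 1200-0066 cannot show who left this study or why. At stake is whether a reader of the primary result can tell how far it depends on the lost patients.

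**Working it through.** **Inputs.** Protocol 9.5 says "we assume the median time on treatment (TOT) on afatinib to be 12 months in this study" and gives the distribution: "Assuming that the time on treatment (TOT) follows an exponential distribution". N = 76 and drop-out is 30%. Milestones: first patient in May 2020, last patient in December 2021, last patient out December 2023. That is about 19 months of accrual plus 24 months, so 24 to 43 months of potential follow-up.

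**Step 1: can the meaning of the 30% be recovered from the plan's 35 events?** The stopping hazard is λ = ln 2 / 12 = 0.0578 per month. With drop-out hazard η, expected events = 76 × λ/(λ+η) × mean of [1 − exp(−(λ+η)t)] over t from 24 to 43.
- No drop-out: the mean of exp(−λt) is (0.250 − 0.083)/(19 × 0.0578) = 0.152, so 76 × 0.848 = 64.5 events.
- Multiplied by 0.7: 45.1 events.
- 30% per year as a competing hazard: 47.2 events. 30% per 24 months: 54.7 events.

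None of these gives 35. The 0.7 version needs 1 − 35/64.5, or about 46% drop-out, to get there. The time base of the 30% therefore cannot be inferred and has to be varied.

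**Step 2: worst-case bound.** If loss is non-informative, the censored analysis returns 12 months. If every drop-out stopped at last contact, the true median is ln 2/(λ+η). The table takes all of the 30% as loss on afatinib.

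| Reading of the 30% | η per month | λ+η | Median (months) | Gap from 12 | Lost on afatinib, of 76 |
|---|---|---|---|---|---|
| per year: −ln 0.7/12 | 0.0297 | 0.0875 | 7.9 | 4.1 | about 24 |
| of patients, before stopping: λ × 0.3/0.7 | 0.0248 | 0.0825 | 8.4 | 3.6 | about 21 |
| per 24 months: −ln 0.7/24 | 0.0149 | 0.0726 | 9.5 | 2.5 | about 14 |
| per 33 months: −ln 0.7/33 | 0.0108 | 0.0686 | 10.1 | 1.9 | about 11 |
| per 43 months: −ln 0.7/43 | 0.0083 | 0.0661 | 10.5 | 1.5 | about 8 |

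Simulated Kaplan-Meier medians at N = 76 agree for the three largest: 11.9 censored against 7.7, 11.9 against 8.2, and 12.0 against 9.4.

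**Step 3: less extreme assumptions.** If half of the drop-outs stopped and the rest were non-informative, the median is ln 2/(λ + η/2). For 30% per 24 months this is 0.693/0.0652 = 10.6 (gap 1.4). For 30% per year it is 0.693/0.0726 = 9.5 (gap 2.5). If none stopped differently from those who remain, the gap is 0.

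**Step 4: opposite direction.** Suppose lost patients all stayed on drug. Then S(t) = 1 − λ/(λ+η) × [1 − exp(−(λ+η)t)]. Setting this to 0.5 gives 13.6 months (30% per 24 months), 15.2 (30% before stopping) and 16.2 (30% per year). The censored median of 12 would then be 1.6 to 4.2 months too short.

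**Step 5: withdrawn patients.** SAP 5.1 censors them. Rule 1 names only loss to follow-up, and Rule 2 does not apply once a patient has left, so Rule 3 makes them events. Yet the last-contact definition under the table includes withdrawn patients, as if they were to be censored. The same patient can be an event or censored depending on which text the programmer follows.

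**The case against.** Several points on the other side stand.

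- A reader might infer that median TOT is overstated by 2.5 to 4 months. The documents do not support that as an expected bias. It needs every drop-out to have stopped at last contact, all of the 30% to occur on afatinib, and a short time base. Follow-up continues through later lines of treatment, and loss after afatinib has ended does not affect TOT.
- A reader might infer that the bias can only lengthen the median. That is not established either. Protocol 9.9.1 expects some patients to transfer care, and an untraced patient may still be taking afatinib. Neither document gives evidence that lost patients usually stop.
- A reader might take 9.11 to claim that attrition bias has been removed. It speaks of efforts, and it refers to Section 9.9, where real tracing is described.
- Lost patients with a known end date are already events under Table 7.6:1, so only those without one are affected.
- Some section numbers (Protocol 9.7.2, SAP 5.3 and 6.4) do not appear in the public text. The absence of a sensitivity analysis can be stated only of what is visible.
- The study is single-arm and descriptive, and Kaplan-Meier censoring is a standard primary choice.

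These points limit the size and certainty of the bias. They do not supply an analysis of the losses that remain after tracing.

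**Conclusion.** The point holds in limited form. Patients lost on afatinib without an end date are censored at a date that can be later than the last dose, the plan expects appreciable drop-out, and nothing visible tests the assumption. Under an exponential TOT with a 12-month median, the overstatement ranges from 0 to a worst case of about 1.5 to 4 months, depending on what the 30% means. It is smaller if part of that drop-out falls after afatinib. The opposite bias is possible.

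These figures place the stop at last contact. An event date at an earlier last dose would shorten the worst-case median further, by an amount the documents do not allow one to calculate.

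The unexplained 35 events might tempt a reader to assume heavier loss and a larger gap. The protocol states 30%, so that inference is not supported. The conflict over withdrawn patients is a plain inconsistency and does not depend on any of these assumptions.

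**What to change.** 1. Keep Kaplan-Meier TOT as the primary analysis, and make SAP 5.1 and Table 7.6:1 agree on how withdrawn patients are handled.
2. Add to SAP 7.6 one pre-specified sensitivity analysis on the Treated Set. Count patients lost or withdrawn while on afatinib as TOT events at their last documented afatinib dose date, or at last known contact if there is none. Report the median and 90% CI beside the primary result and describe them as a worst-case bound. The last-dose date is already used in SAP 7.6; dispensing dates are not among the listed variables and should not be relied on.
3. In Protocol 9.11, limit the 1200-0066 comparison to channelling, and cite the 9.9.1 tracing and this analysis for attrition.

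The cost is one extra Kaplan-Meier run, small wording changes, and a second, shorter median in the report.
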